11.7.2 Analysis of Adverse Events

Adverse events will be summarized using the number and percentage of subjects with AEs for all subjects in the safety population. Summaries will also be provided for subgroups including Region, Age, Gender and Race.

All AEs will be coded using MedDRA. Treatment-emergent and post-treatment AEs will be summarized by System Organ Class and Preferred Term for each treatment group. Adverse events will also be summarized by their maximum severity.

Summaries will also be provided for the following types of AEs:

- SAEs
- Related AEs (including all categories for relationship to study medication other than “Unrelated”, as determined by the Investigator)
- AEs leading to early discontinuation of study medication

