7.5 Study Completion, Subject Completion, Study Discontinuation, and Withdrawal of Subjects

7.5.1 Study Completion

The study will be considered completed (end of trial) when approximately 631 MACE events have accrued over the 2 NDD-CKD studies (Studies AKB-6548-CI-0014 and AKB-6548-CI-0015) and all enrolled subjects have had the opportunity to have their Visit 13 (+/- 5 days). These 2 NDD-CKD studies were sized based on power considerations for the primary safety analysis of MACE events, and thus each study is highly powered (>90%) for the primary and key secondary efficacy analysis. Thus, primary efficacy analyses will be based on the randomized population and every subject will have completed the primary evaluation period (Weeks 24-36).

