7.5.5 Individual Subject Discontinuation

During this study, it is anticipated that some subjects may permanently discontinue study medication (vadadustat or darbepoetin alfa) for any of the following reasons:

- Unacceptable toxicity or drug intolerability
- Investigator discretion
- Subject withdrawal of consent
- Subject becomes pregnant
- Receipt of a kidney transplant

- Lack of efficacy
- Other reasons.

Lack of efficacy is defined as inadequate response to darbepoetin alfa or vadadustat in the Investigator's opinion.

Subjects who undergo a solid organ (including kidney), hematopoietic stem cell, or bone marrow transplantation will have their study medication (vadadustat or darbepoetin alfa) permanently discontinued.

See [Section 9.4, Study Medication Stopping Rules](#) for additional details on the management of subjects with ALT and AST abnormalities.

It is important to continue to follow subjects that permanently discontinue study medication. Please see Sections 7.5.5.1, Temporary Interruption of Study Medication and 7.5.5.2, Permanent Discontinuation of Study Medication and [Appendix A: Schedule of Activities](#)).

Receipt of rescue therapy is not a reason for permanent study medication discontinuation. While receiving ESA rescue, subjects must temporarily discontinue study medication (vadadustat or darbepoetin alfa), but should resume study medication once rescue therapy has ended, as detailed in [Section 8.4.7, Rescue Therapy](#).

As part of the informed consent process, only subjects who fully understand and agree to full participation and long-term follow-up should be consented to participate.

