7.5.5.2 Permanent Discontinuation of Study Medication

Subjects who permanently discontinue study medication prior to global study completion are expected to continue to be followed post discontinuation of study medication. These subjects are to have their EOT visit at the time of permanent discontinuation of study medication, have the Follow-up visit 4 weeks after EOT visit and continue to be followed through global study completion. At global study completion, each subject will have an End of Study (EOS) assessment to complete participation in the study. Receipt of rescue therapy is not a reason for permanent study medication discontinuation. While receiving ESA rescue, subjects must temporarily discontinue study medication but should resume study medication following the end of rescue therapy.

For subjects who permanently discontinue study medication, the Investigator will resume standard of care treatment, including ESAs and iron therapy, as deemed appropriate.

It is important to continue to follow subjects that permanently discontinue study medication.

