10.3.1 Reporting Period

The AE reporting period for this study begins from time of randomization through global study completion.

In addition, any AE that occurs subsequent to the AE reporting period that the Investigator assesses as related to the study medication should also be reported as an AE.

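### Section 11.7.2 reports AEs only as crude percentages, which would favour whichever arm stops drug earlier if the arms discontinue at different rates

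*Protocol*

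**What the plan says.** All references are to the amended protocol (Amendment 7).

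- **Statistic.** Section 11.7.2, for the safety population: "Adverse events will be summarized using the number and percentage of subjects with AEs". It adds: "Treatment-emergent and post-treatment AEs will be summarized by System Organ Class and Preferred Term for each treatment group". SAEs, related AEs and AEs leading to discontinuation of study medication are also summarized. Neither treatment-emergent nor post-treatment is defined. Section 11.7.3 defers its detail to the SAP; 11.7.2 does not.
- **Collection.** Section 10.3.1: "The AE reporting period for this study begins from time of randomization through global study completion".
- **Length of follow-up.** Section 7.5.1: "The study will be considered completed (end of trial) when approximately 631 MACE events have accrued over the 2 NDD-CKD studies", with the further condition that "all enrolled subjects have had the opportunity to have their Visit 13 (+/- 5 days"). Appendix A places Visit 13 at Week 36 and schedules visits to Week 208.
- **After permanent discontinuation.** Section 7.5.5.2 expects subjects to "continue to be followed through global study completion". Section 7.5.5.4 leaves the visit schedule to agreement between investigator and subject. It makes end-of-study status the only mandatory item and lists AE assessment as optimal.
- **Reasons for stopping.** Section 7.5.5: "Lack of efficacy is defined as inadequate response to darbepoetin alfa or vadadustat in the Investigator's opinion". Section 9.4 lists liver-test results that require permanent discontinuation. Treatment is open-label (8.4.3).

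**The concern.** A crude percentage combines two things: how fast events occur and how long subjects were at risk of being counted. When counting stops at or near the last dose, an arm that leaves treatment sooner has less time in which an event can be recorded. It then shows a lower percentage even if the drugs are equally toxic per unit of time. The separate post-treatment table does not repair this. It moves the other way when capture is complete, and it may be thin when AE assessment after stopping is optional.

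The AE and SAE tables carry much of this study's own evidence on harms other than the adjudicated endpoints, so a distorted arm contrast there would matter to a reader of the study report.

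**Working it through.** **The plan's own figure.** Section 11.7.2 gives no number to reproduce. The count that drives closure does reproduce. With margin 1.25, true hazard ratio 1, a two-sided 95% interval and 80% power, Schoenfeld's formula gives `4 x (1.960 + 0.842)^2 / (ln 1.25)^2 = 631`. Nothing below depends on it.

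**Inputs from the protocol:** 1:1 allocation; about 925 subjects per arm (8.4.1); earliest closure at about Week 36, roughly 0.7 years.

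**Inputs that are assumptions, because the protocol gives none:**
- AE rate `l`, constant and equal in both arms: 0.2 per year, with 0.1 and 0.5 as the range.
- Time from entry to closure `t`, uniform from 0.7 to 3.0 years.
- Discontinuation hazard `d`: 0.20 per year in arm A; 0.20, 0.30 or 0.40 per year in arm B.
- Treatment-emergent counting ends when drug stops.

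**Formula.** The probability of a first AE before the earlier of drug stop and closure is `l/(l+d) x (1 - exp(-(l+d) t))`. Averaged over `t` uniform on 0.7 to 3.0, it becomes `l/(l+d) x [1 - (exp(-0.7(l+d)) - exp(-3.0(l+d))) / (2.3(l+d))]`.

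**Worked at l = 0.2:**
- d = 0.20: `0.5 x [1 - (0.7558 - 0.3012)/0.92]` = 25.3%
- d = 0.30: `0.4 x [1 - (0.7047 - 0.2231)/1.15]` = 23.3%
- d = 0.40: `0.333 x [1 - (0.6570 - 0.1653)/1.38]` = 21.5%

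Mean time on drug in these three cases is 1.52, 1.38 and 1.26 years.

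**Crude on-drug percentages, arm A versus arm B:**

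| AE rate per year | d 0.20 v 0.20 | d 0.20 v 0.30 | d 0.20 v 0.40 |
|---|---|---|---|
| 0.1 | 13.8 v 13.8 | 13.8 v 12.6 | 13.8 v 11.6 |
| 0.2 | 25.3 v 25.3 | 25.3 v 23.3 | 25.3 v 21.5 |
| 0.5 | 49.7 v 49.7 | 49.7 v 46.2 | 49.7 v 43.1 |

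The ratio B/A is 0.92 to 0.93 in the third column and 0.84 to 0.87 in the last. With 925 per arm, the chance that such a gap looks nominally significant is 11%, 17% and 33% (third column) and 29%, 50% and 81% (last column), reading down. Section 11.7.2 plans no test, so these figures only gauge how readily the gap would be noticed. Fixing closure at 1.8 years for everyone changes little: at 0.2 per year, 25.7% versus 23.7% or 22.0%.

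**The same data per subject-year.** Expected time at risk to first event is `(1 - exp(-(l+d) t))/(l+d)`. Expected first events divided by that time equals `l`, whatever `d` is. At 0.2 per year both arms show 20 per 100 subject-years in every scenario.

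**Counting to study completion.** If AEs were fully captured from randomization to closure regardless of drug stop, both arms would show 30.3% at 0.2 per year, whatever the discontinuation rates.

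**The case against.** The strongest reply is that this belongs to the SAP. Section 11.7.2 is a short summary. It names counts and percentages but does not exclude rates, and exposure-adjusted tables are ordinary SAP content. That stands to this extent: their absence from the protocol is not an error in itself. What remains is that 11.7.2 names the statistic and, unlike 11.7.3, does not hand the detail on.

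Three stronger readings are tempting, and the protocol does not support them.

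- **That event-driven follow-up biases the comparison.** The spread from about Week 36 to Week 208 is between subjects. Closure applies alike to both randomized arms, and the gap is zero when discontinuation is equal.
- **That AEs are counted only on drug.** Treatment-emergent is undefined. Listing it beside post-treatment suggests a window ending near the last dose, but collection runs to global completion and post-treatment AEs are also tabulated.
- **That the arms will differ in time on drug.** No section says so. The lack-of-efficacy definition and the liver rules are worded for both drugs. They show only that equal exposure cannot be presumed.

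The size can also be overstated. Giving every subject in an arm the same time on drug, say 1.2 versus 1.5 years at 0.3 events per year, yields `1 - exp(-0.36)` = 30.2% against `1 - exp(-0.45)` = 36.2%. Letting time on drug vary exponentially with the same means yields `0.36/1.36` = 26.5% against `0.45/1.45` = 31.0%, a smaller gap.

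Finally, section 11.7.1 already uses time-to-event methods for MACE, its components, thromboembolic events, heart-failure hospitalization and expanded MACE, and repeats MACE with censoring 4 weeks after drug stop. The point is therefore confined to the remaining AEs.

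**Conclusion.** The point holds in a conditional form. Section 11.7.2 names a statistic that cannot separate event rate from time on drug, in a trial where time on drug varies widely and AE capture after stopping may be incomplete. Distortion between arms needs two things the protocol does not state: a treatment-emergent window that ends near the last dose, and different discontinuation rates. Given both, 1.5 to 2 times the discontinuation hazard lowers the crude percentage by about 7% to 16% in relative terms at equal toxicity, or 2.0 to 3.8 percentage points at 0.2 events per year. Without differential discontinuation, the effect on the comparison is nil. The AE rates, discontinuation hazards and entry spread are all assumed. This is an inexpensive improvement to the safety display; it does not invalidate the planned tables.

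**What to change.** In section 11.7.2:

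1. Define treatment-emergent by stating the risk window after the last dose. The 4-week window already used for the MACE analysis in 11.7.1 is an obvious candidate, but the choice is the sponsor's.
2. Keep the percentages. For treatment-emergent AEs, SAEs and related AEs, add exposure-adjusted incidence by arm: subjects with a first event per 100 subject-years at risk, with time at risk ending at the first event, the end of the window or the end of follow-up. Label it a descriptive display.

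AEs leading to discontinuation are left out because the event itself ends exposure.

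The cost is extra table columns built from dose and event dates that the study already needs; no new data and no patient burden. The drawback is that subject-year rates assume a roughly constant hazard and can mislead for AEs concentrated early in treatment, which is why the percentages should stay. If the SAP already plans such rates, the only change needed is to bring 11.7.2 into line with it.

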11.7.3 Remaining Safety Endpoints

The analysis of the following safety endpoints will be detailed in the SAP:

The analysis of proportion of subjects with Hb >12.0 g/dL, >13.0 g/dL, or >14.0 g/dL post-Baseline will classify a subject as a “yes” if:

- Any value Hb >12.0 g/dL at any time after Day 1
- Any confirmed value Hb >12.0 g/dL at any time after Day 1
- Any value Hb >13.0 g/dL at any time after Day 1
- Any confirmed value Hb >13.0 g/dL at any time after Day 1
- Any value Hb >14.0 g/dL at any time after Day 1
- Any confirmed value Hb >14.0 g/dL at any time after Day 1

An Hb value above a set threshold will be considered as confirmed if there are 2 consecutive values above that threshold. The second of the 2 consecutive assessments should be done at most 12 weeks after the first assessment. Subjects with no available data post-Baseline will be excluded from this analysis. All other subjects will be classified to the “no” category.

The analysis of proportion of subjects with any Hb increase >1.0 g/dL within any 2-week interval or >2.0 g/dL within any 4-week interval post-Baseline will classify a subject as a “yes” if at least 1 of the following criteria at any point after Day 1 is met:

- Hb increase >1.0 g/dL within any 2-week interval
- Hb increase >2.0 g/dL within any 4-week interval

Subjects with no available data post-Baseline will be excluded from this analysis. All other subjects will be classified to the “no” category.

Observed values of continuous and categorical parameters and changes from Baseline for continuous parameters to each study visit will be summarized descriptively for vital signs and clinical laboratory results. Graphical displays of selected laboratory parameters will also be provided.

11.8 Additional Assessments

11.8.1 Concomitant Medications

Prior and concomitant medications will be coded using World Health Organization (WHO) Drug dictionary.

Prior medications will be defined as any medications that were taken before the date of the first dose of study medication. Concomitant medications will be defined as any medications taken at any time from the date of the first dose of study medication through the date of the last dose of the study medication.

11.8.2 Biomarkers

Biomarkers (including, but not limited to, hepcidin and VEGF) will be summarized descriptively at Baseline and by visit post-Baseline.

11.8.3 Pharmacokinetics

Descriptive and graphical summaries will be generated for PK measurements.

12 DATA HANDLING AND RECORD KEEPING

12.1 Case Report Forms/Electronic Data Capture

This study will utilize an EDC system to manage data collection during this trial. The system is fully Code of Federal Regulations 21 part 11 compliant. An EDC system contains certain functionality including, but not limited to, a graphical user interface to help facilitate data entry, a data validation element to check user data, and a reporting function to assist with the review and analysis of data. Case report forms available through this system are required and should be completed for each randomized subject.

Any form of data from the electronic system are the sole property of the Sponsor and should not be made available in any form to third parties, except for authorized representatives of the Sponsor or appropriate regulatory authorities, without written permission from the Sponsor.

The Investigator has ultimate responsibility for the accuracy, authenticity, and timely collection and reporting of all clinical, safety, and laboratory data entered in the EDC or any other data collection forms. The CRFs must be signed electronically by the Investigator to attest that the data contained on the CRFs is true.

In most cases, the source documents are contained in the subject's chart at the hospital or the physician's office. In these cases, data collected on the CRFs must match the data in those charts.

12.2 Record Retention

To enable evaluations and/or audits from regulatory authorities or the Sponsor, the Investigator agrees to keep records, including the identity of all participating subjects (sufficient information to link records, eg, CRFs and hospital records), all original signed informed consent forms, copies of all CRFs, SAE forms, source documents, detailed records of drug disposition, and adequate documentation of relevant correspondence (eg, letters, meeting minutes, telephone calls reports). The records should be retained by the Investigator according to the International Conference on Harmonization (ICH), local regulations, or as specified in the Clinical Study Agreement, whichever is longer.

If the Investigator becomes unable for any reason to continue to retain study records for the required period (eg, retirement, relocation), the Sponsor should be prospectively notified. The study records must be transferred to a designee acceptable to the Sponsor, such as another Investigator, another institution, or to the Sponsor. The Investigator must obtain Sponsor's written permission before disposing of any records, even if retention requirements have been met.

13 QUALITY CONTROL (QC) AND QUALITY ASSURANCE (QA)

13.1 Investigative Site Monitoring Visits

During study conduct, the Sponsor or its agent will conduct periodic monitoring visits to ensure that the protocol and Good Clinical Practice (GCP) are being followed. The monitors will review source documents to confirm that the data recorded on the CRFs is accurate. The Investigator/institution will allow the Sponsor's monitors or designees and appropriate regulatory authorities direct access to source documents to perform this verification.

The investigative site may also be subject to quality assurance audits performed by the Sponsor or companies working with or on behalf of the Sponsor, and/or review by the IRB/IEC, and/or to inspection by appropriate regulatory authorities.

It is important that the Investigator(s) and their relevant personnel are available during the monitoring visits and possible audits or inspections and that sufficient time is devoted to the process.

13.2 Protocol Deviations

The Investigator will not deviate from the protocol, except where necessary to eliminate an immediate hazard to study subjects. Should other unexpected circumstances arise that will require deviation from protocol-specified procedures, the Investigator will consult with the Sponsor or designee (and IRB or IEC, as required) to determine the appropriate course of action.

The investigative site should document all protocol deviations in the subject's source documents. In the event of a significant deviation, the investigative site should notify the Sponsor or its designee (and IRB or IEC, as required). Significant deviations include, but are not limited to, those that involve fraud or misconduct, increase the health risk to the subject, or confound interpretation of primary study assessments.

14 STUDY DISCONTINUATION/INVESTIGATIVE STUDY SITE TERMINATION

The Sponsor reserves the right to discontinue the study prior to inclusion of the intended number of subjects but intends only to exercise this right for valid scientific or administrative reasons. After such a decision, the Investigator must contact all participating subjects within a time period specified by the Sponsor to inform them of the decision to discontinue the study.

14.1 Criteria for Premature Termination or Suspension of the Study

The following criteria may result in either temporary suspension or early termination of the study:

- New information regarding the safety or efficacy of the study medication that indicates a change in the known risk/benefit profile for the compound, such that the risk/benefit is no longer acceptable for subjects participating in the study.
- Significant violation of GCP that compromises the ability to achieve the primary study objectives or compromises subject safety.

The Sponsor reserves the right to discontinue the study for other valid administrative reasons.

14.2 Criteria for Premature Termination or Suspension of Investigational Study Sites

A study site may be terminated prematurely or suspended if the study site (including the Investigator) is found to be in significant violation of GCP, protocol, contractual agreement, or is unable to ensure adequate performance of the study.

14.3 Procedures for Premature Termination or Suspension of the Study or Investigational Sites

In the event that the Sponsor elects to terminate or suspend the study or the participation of an investigational study site, a study-specific procedure for early termination or suspension will be provided by the Sponsor; the procedure will be followed by applicable investigational study sites during the course of termination or study suspension.

15 ETHICS

15.1 Ethical Conduct of the Study

The study will be conducted in accordance with the Declaration of Helsinki on Ethical Principles for Medical Research Involving Human Subjects, adopted by the General Assembly of the World Medical Association (2013).

In addition, the study will be conducted in accordance with the protocol, the ICH guideline on GCP, and applicable local regulatory requirements and laws.

15.2 Institutional Review Board/Independent Ethics Committee

It is the responsibility of the Investigator to have prospective approval of the study protocol, protocol amendments, informed consent forms, and other relevant documents, (eg, recruitment advertisements, if applicable) from the IRB/IEC. All correspondence with the IRB/IEC should be retained in the Investigator File. Copies of IRB/IEC approvals should be forwarded to the Sponsor or its designee.

In case of substantial protocol amendment, the Sponsor will obtain approval from responsible Regulatory Authorities before implementation.

The only circumstance in which an amendment may be initiated prior to IRB/IEC approval is where the change is necessary to eliminate apparent immediate hazards to the subjects. In that event, the Investigator must notify the IRB/IEC and the Sponsor in writing immediately after the implementation.

15.3 Subject Information and Consent

It is the responsibility of the Investigator to give each subject (or the subject's acceptable representative), prior to inclusion in the study, full and adequate verbal and written information regarding the objective and procedures of the study and the possible risks involved. The subjects must be informed about their right to withdraw from the study at any time.

Furthermore, it is the responsibility of the Investigator, or a person designated by the Investigator, to obtain signed informed consent from each subject or the subject's legally acceptable representative prior to inclusion in the study. The Investigator will retain the original of each subject's signed consent form.

The informed consent forms will be in compliance with ICH GCP, local regulatory requirements, and legal requirements. The informed consent forms used in this study, and any changes made during the course of the study, must be prospectively approved by both the IRB/IEC and the Sponsor before use.

15.4 Reporting of Safety Issues and Serious Breaches of the Protocol or ICH GCP

In the event of any prohibition or restriction imposed (ie, clinical hold) by an applicable Competent Authority, or if the Investigator is aware of any new information which might influence the evaluation of the benefits and risks of the investigational product, the Sponsor should be informed immediately.

In addition, the Investigator will inform the Sponsor immediately of any urgent safety measures taken by the Investigator to protect the study subjects against any immediate hazard, and of any serious breaches of this protocol or of ICH GCP, defined as a breach that will likely affect the safety or physical or mental integrity of subjects or the scientific value of the trial, that comes to the attention of the Investigator.

